3.4.7 Safety analyses

3.4.7.1 Adverse events

All AEs reported during the trial will be listed, documenting course, severity, investigator assessment of the relationship to the IMPs, and outcome. AEs will be coded using the MedDRA mapping system for PTs and SOC.

TEAEs, i.e. AEs with an onset (or worsening) on or after the time of the first IMP application will be summarized by the number of TEAEs and number (percent) of patients reporting TEAEs by primary SOC, PT, severity, and relationship to IMP. When summarizing TEAEs by severity or relationship to IMP, each subject will be counted once within a SOC or a PT by using the event with the greatest severity or with the strongest relationship to IMP, respectively, within each category.

Listings of serious adverse events (SAE) and patients who prematurely discontinued treatment due to AEs will be given.

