3.2 Stress/risks due to the investigational medicinal product (IMP)

General safety and tolerability of MP1032 has been assessed in one phase 1 first-in-man clinical trial. In the single ascending doses part of this trial, twelve volunteers were administered 50 to 600 mg MP1032. One mild ADR ("headache") was reported once after treatment with 50 mg MP1032 in one volunteer. No ADRs were reported in the multiple ascending doses part where volunteers received 2×100 mg per day and 2×300 mg per day at 12-hour intervals for seven consecutive days.

In a previous IIa trial following TEAEs were observed: In summary the number of patients with TEAEs was 14 (60.87%, 27 TEAEs) in the MP1032 group and 15 (65.22%, 32 TEAEs) in the placebo group. The most commonly reported TEAEs were in the SOC categories of infections and infestations (5 patients [21.74%] in the MP1032 group and 8 patients [34.78%] in the placebo group) and nervous system disorders (7 patients [30.43%] in the MP1032 group and 3 patients [13.04%] in the placebo group). No clinically important differences were seen between the two treatment groups with regard to the number and overall pattern of patients reporting TEAEs by System Organ Class (SOC).

A positive phototoxic signal detected in non-clinical studies could be indicative of a likely clinical phototoxic risk of MP1032, although the risk for the patients seems to be unlikely and no associated TEAEs were seen in the previous clinical trials. Nevertheless, psoriasis patients participating in this trial should be advised to minimize sun exposure (sun bathing) and strong UV exposure (see also inclusion criterion No. 9). Furthermore, the use of sunscreen will be recommended when spending an extended period of time outdoors. The latter requirement will be valid during the whole 12 weeks of treatment duration plus the 4 weeks of follow up period.

Women of childbearing potential (WCBP) must agree to use a highly effective contraceptive method (Pearl-Index < 1%) starting at screening and continuing throughout the clinical trial period and for 28 days after final IMP administration.

Highly effective forms of birth control (according to International Conference on Harmonization [ICH] M3) have low failure rates (i.e. less than 1% per year) when used consistently and correctly, and include the following:

- The male partner of a female patient has undergone effective surgical sterilization.

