The trial is designed with two primary endpoints as described in the EMA guideline [2].

Table 1: Objectives and endpoints:

Primary objective	Primary endpoint

The primary objective of this trial is to evaluate the clinical efficacy and safety of two oral doses of MP1032 (150 mg bid and 300 mg bid) when taken for 12 weeks by patients with moderate-to-severe chronic plaque psoriasis.
	
Efficacy: MP1032 300 mg bid vs. placebo
 
 1. Percentage of patients who achieve a 75% improvement (response) in their PASI score (PASI 75) at Week 12 (Day 84) compared to baseline treated with 300 mg bid of MP1032 compared to placebo 2. Improvement (1 or more points on a 7 Point Scale) in PGA at Week 12 (Day 84) compared to baseline treated with 300 mg bid of MP1032 compared to placebo 
Efficacy: MP1032 150 mg bid vs. placebo
 
 3. Percentage of patients who achieve a 75% improvement (response) in their PASI score (PASI 75) at Week 12 (Day 84) compared to baseline treated with 150 mg bid of MP1032 compared to placebo 4. Improvement (1 or more points on a 7 Point Scale) in PGA Score at Week 12 (Day 84) compared to baseline treated with 150 mg bid of MP1032 compared to placebo 
Safety:
 
 5. Incidence of adverse events

Secondary objectives	Secondary endpoints
To evaluate the effect of each oral doses of MP1032 (150 mg bid and 300 mg bid) compared to placebo on the PASI score	
 Percentage of patients who achieve a 50% improvement (response) in their PASI score (PASI 50) at Week 12 (Day 84) compared to baseline treated with 300 mg bid of MP1032 compared to placebo Percentage of patients who achieve a 50% improvement (response) in their PASI score (PASI 50) at Week 12 (Day 84) compared to baseline treated with 150 mg bid of MP1032 compared to placebo Mean PASI score and change to baseline at Week 4 (Day 28), 8 (Day 56), 12 (Day 84) and week 16 (Day 112) Time to achieve PASI 50 and PASI 75 Mean PASI score and change from Baseline at Week 4 (Day 28), 8 (Day 56), 12 (Day 84) and 16 (Day 112)
To evaluate the effect of each oral dose of MP1032 (150 mg bid and 300 mg bid) compared to placebo on the PGA score	Mean score and change from Baseline at Week 4 (Day 28), 8 (Day 56), 12 (Day 84) and 16 (Day 112) in the PGA

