1.2 Objectives

The trial is designed with two primary endpoints as described in the EMA guideline [2].

Table 1 Objectives and endpoints:

Primary objective	Primary endpoint
The primary objective of this trial is to evaluate the clinical efficacy and safety of two oral doses of MP1032 (150 mg bid and 300 mg bid) when taken for 12 weeks by patients with moderate-to-severe chronic plaque psoriasis.	
Efficacy: MP1032 300 mg bid vs. placebo
 
1.1 Percentage of patients who achieve a 75% improvement (response) in their PASI score (PASI 75) at Week 12 (Day 84) compared to baseline in patients treated with 300 mg bid of MP1032 compared to placebo
 
1.2 Improvement (1 or more points on a 7 Point Scale) in PGA at Week 12 (Day 84) compared to baseline in patients treated with 300 mg bid of MP1032 compared to placebo
 
Efficacy: MP1032 150 mg bid vs. placebo
 
2.1 Percentage of patients who achieve a 75% improvement (response) in their PASI score (PASI 75) at Week 12 (Day 84) compared to baseline in patients treated with 150 mg bid of MP1032 compared to placebo
 
2.2 Improvement (1 or more points on a 7 Point Scale) in PGA Score at Week 12 (Day 84) compared to baseline in patients treated with 150 mg bid of MP1032 compared to placebo
 
Safety:
 
3 Incidence of adverse events

Secondary objectives	Secondary endpoints
To evaluate the effect of each oral doses of MP1032 (150 mg bid and 300 mg bid) compared to placebo on the PASI score	
 Percentage of patients who achieve a 50% improvement (response) in their PASI score (PASI 50) at Week 12 (Day 84) compared to baseline in patients treated with 300 mg bid of MP1032 compared to placebo Percentage of patients who achieve a 50% improvement (response) in their PASI score (PASI 50) at Week 12 (Day 84) compared to baseline in patients treated with 150 mg bid of MP1032 compared to placebo Mean PASI score and change from baseline at Week 4 (Day 28), 8 (Day 56), 12 (Day 84) and week 16 (Day 112) Time to achieve PASI 50 and PASI 75
To evaluate the effect of each oral dose of MP1032 (150 mg bid and 300 mg bid) compared to placebo on the PGA score	
 Mean score and change from Baseline at Week 4 (Day 28), 8 (Day 56), 12 (Day 84) and 16 (Day 112) in the PGA

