3.4 Statistical methods

Statistical analyses will be performed using two-sided tests, without adjustment for multiplicity. All p-values will be interpreted descriptively.

Data will be summarized by treatment group (and by visit when applicable), with respect to demographic and baseline characteristics, efficacy variables, and safety variables.

Summary statistics will include the mean, number of non-missing cases (n), standard deviation, median, minimum, and maximum values for continuous variables, and frequencies and percentages for categorical variables.

Categorical efficacy variables will be analyzed using the Cochran-Mantel-Haenszel (CMH) test with stratification by (pooled) analysis center and the Fisher's exact test in case of analyses without stratification (mainly for safety assessment).

Selected scores will be analyzed using an analysis of covariance (ANCOVA) model, with treatment group and (pooled) analysis center as factors and baseline outcome as covariate.

Time to event data will be analyzed using the Kaplan-Meier method, and treatment group differences will be tested by the log-rank test.

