3.4.6 Efficacy analyses

3.4.6.1 Hypotheses

Since this is an exploratory trial no formal hypotheses are postulated. The data will be evaluated descriptively.

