3.4.6.2 Statistical analyses

Primary efficacy endpoints

The co-primary endpoint response in PASI 75 at Week 12 (Day 84) is defined as 75% improvement in PASI score compared to baseline (i.e. percent of change from baseline $\leq 75\%$). The co-primary endpoint improvement in PGA at Week 12 (Day 84) is defined as reduction by 1 or more points on the PGA scale in comparison to baseline.

The comparisons of the treatment groups MP1032 300 mg bid and MP1032 150 mg bid, each vs. the placebo treatment, with respect to each, the PASI 75 rate and PGA improvement rate, at Week 12 (Day 84) will be evaluated by the CMH test stratified by (pooled) analysis center. The common odds-ratio with 95% confidence interval will be provided. The homogeneity of the individual odds-ratios will be assessed by the Breslow-Day test.

Secondary efficacy endpoints

Secondary efficacy endpoints will be evaluated descriptively. The methodology outlined at the top of this section 3.4.6.2 will be applied for pairwise treatment comparisons vs. placebo:

The PASI 50 responder rate at Week 12 (Day 84) will be evaluated according to the primary efficacy endpoints, as well as the PASI 75, PASI 50 and PGA improvement at Week 4 (Day 28) and Week 8 (Day 56) of the treatment phase and at follow-up, 4 weeks after end of treatment.

The change in the PASI score from baseline to each post baseline visit, respectively, will be evaluated using an analysis of covariance (ANCOVA) model, with treatment group and (pooled) analysis center as factors and baseline outcome as covariate, in both analysis sets, FAS and VCS.

The time to achievement of PASI 50 and PASI 75, respectively, will be evaluated using the Kaplan-Meier method. The study day of first achievement of PASI 50 and PASI 75, respectively, will be the considered event, with study day of last assessment as the time point of censoring, in case of no occurrences of PASI 50 or PASI 75. Pairwise treatment group differences will be tested by the log-rank test.

Location shift in change from baseline in PGA will be assessed using Hodges-Lehmann Estimation with comparison by the Wilcoxon rank sum test, in both analysis sets, FAS and VCS.

Descriptive summaries will be provided for each parameter by treatment group and by visit, if applicable. Percentages will be provided based on the number of non-missing cases, if not otherwise stated. For PASI and PGA the descriptive summaries will be performed in both analysis sets, FAS and VCS.

Subgroup analyses

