² Incidence determined as the number of subjects with respective AE

³ Incidence rate determined as the incidence divided by the number of subjects at risk, i.e. size of the SES

⁴ AEs not seen before treatment or, if already present before treatment, worsened after start of treatment

⁵ Subjects counted once under the highest intensity or the strongest relation to the IMP

Source data: <DATASET> <DATE>
Program: <SAS PROGRAM> <DATE>

Table 14.5.2: TEAEs by MedDRA terminology – Summary (SES)
(Part 1 of 1)

TEAEs¹ by MedDRA terminology Count² / Incidence³ (Incidence rate%⁴)	MP1032 300 mg bid (N = XX)	MP1032 150 mg bid (N = XX)	Placebo bid (N = XX)
System organ class / Preferred term⁵			
<System organ class A>	XXX / XX (XXX.X%)	XXX / XX (XXX.X%)	XXX / XX (XXX.X%)
<Preferred term 1>	XXX / XX (XXX.X%)	XXX / XX (XXX.X%)	XXX / XX (XXX.X%)
<Preferred term 2>	XXX / XX (XXX.X%)	XXX / XX (XXX.X%)	XXX / XX (XXX.X%)
<System organ class B>	XXX / XX (XXX.X%)	XXX / XX (XXX.X%)	XXX / XX (XXX.X%)
<Preferred term 1>	XXX / XX (XXX.X%)	XXX / XX (XXX.X%)	XXX / XX (XXX.X%)
<Preferred term 2>	XXX / XX (XXX.X%)	XXX / XX (XXX.X%)	XXX / XX (XXX.X%)
<System organ class C>	XXX / XX (XXX.X%)	XXX / XX (XXX.X%)	XXX / XX (XXX.X%)
<Preferred term 1>	XXX / XX (XXX.X%)	XXX / XX (XXX.X%)	XXX / XX (XXX.X%)
<Preferred term 2>	XXX / XX (XXX.X%)	XXX / XX (XXX.X%)	XXX / XX (XXX.X%)

¹ AEs not seen before treatment or, if already present before treatment, worsened after start of treatment

² Count of adverse events reported

³ Incidence is determined as the number of subjects with any respective adverse event

⁴ Incidence rate is determined as the incidence divided by the number of subjects at risk, i.e. size of the safety population

⁵ Coded using MedDRA dictionary (version 20.1 from March 2018), sorted alphabetically.

Source data: <DATASET> <DATE>

Program: <SAS PROGRAM> <DATE>

Table 14.5.3: TEAEs by MedDRA terminology and severity – Summary (SES)
(Part 1 of 1)

TEAEs ¹ by MedDRA terminology Count ² / Incidence ³ (Incidence rate%) ⁴)	Severity	MP1032 300 mg bid (N = XX)	MP1032 150 mg bid (N = XX)	Placebo bid (N = XX)
System organ class / Preferred term⁵				
<System organ class A>	Mild	XXX / XX (XXX.X%)	XXX / XX (XXX.X%)	XXX / XX (XXX.X%)
	Moderate	XXX / XX (XXX.X%)	XXX / XX (XXX.X%)	XXX / XX (XXX.X%)
	Severe	XXX / XX (XXX.X%)	XXX / XX (XXX.X%)	XXX / XX (XXX.X%)

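### Adverse event incidence is a primary endpoint, but the SAP plans no between-arm estimate or interval for it and assigns the announced Fisher's exact test to no adverse event table

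*SAP*

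**What the plan says.** The primary objective covers both efficacy and safety of the two doses. The safety endpoint under it is "3 Incidence of adverse events" in SAP 1.2, Table 1, and "5. Incidence of adverse events" in Table 1 of Protocol Section 4.

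For its analysis, SAP 3.4.7.1 says that TEAEs will be "summarized by the number of TEAEs and number (percent) of patients reporting TEAEs by primary SOC, PT, severity, and relationship to IMP". Shells 14.5.1 to 14.5.4 in the SAP Appendix match this. Each cell holds an event count, a number of patients and a percentage, and a footnote to Table 14.5.1 gives the denominator: "Incidence rate determined as the incidence divided by the number of subjects at risk, i.e. size of the SES". These shells contain no row comparing a dose with placebo.

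The general methods in SAP 3.4 name "the Fisher's exact test in case of analyses without stratification (mainly for safety assessment", and Protocol 6.5 says the same. No later safety section of the SAP takes it up. SAP 1.3 records no modification of the protocol's statistical section.

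For the primary efficacy endpoints, SAP 3.4.6.2 states: "The common odds-ratio with 95% confidence interval will be provided". Their shells (for example Table 14.3.3) carry a block comparing each dose with placebo. So do the subgroup shells for change in PASI and PGA (Tables 14.4.1 to 14.4.22).

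**The concern.** A placebo-controlled trial with safety in its primary objective would normally estimate the excess of adverse events on each dose over placebo and state how precise that estimate is. Here the reader gets three percentages side by side and must judge informally whether a gap is noise or a signal. At this sample size, the same pair of percentages can be compatible both with no excess and with a large one.

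There is also a gap inside the plan. A programmer working from the shells would never run Fisher's test. An analyst working from SAP 3.4 could decide after unblinding which adverse event rows to test. Even if the test were run, a p-value alone would give neither the size of a difference nor its precision.

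**Working it through.** **The plan's own figure.** The only operating figure in the documents concerns efficacy: 80% power with 40 per group for 0.674 v 0.40, chi-square test, two-sided 0.10. The usual normal approximation uses p̄ = 0.537 and gives:

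z = [0.274 × √40 − 1.645 × √(2 × 0.537 × 0.463)] / √(0.674 × 0.326 + 0.40 × 0.60) = (1.733 − 1.160) / 0.678 = 0.845

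That is a power of 80.1%, so the figure reproduces. No power or precision figure is stated for adverse events.

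**Inputs for the illustration.** The planned size is about 50 randomized per arm (SAP 2.1). The safety set takes everyone dosed, so 50 is the relevant denominator, and 40 is shown as a lower case. The rates are borrowed from Phase IIa as reported in Protocol 3.2:
- Any TEAE: 60.87% v 65.22%.
- "nervous system disorders (7 patients [30.43%] in the MP1032 group and 3 patients [13.04%] in the placebo group".

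Applying these rates here is an assumption. Phase IIa used 100 mg twice daily for 42 days, and this trial uses other doses for 12 weeks. The percentages also imply 23 patients per group (14/0.6087 = 23; 15/0.6522 = 23), 46 in total, while Protocol Section 2 says 44 were randomized. The rates serve only to show precision.

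**Expected counts at 50 per arm.**
- Any TEAE: 50 × 0.6087 = 30.4 and 50 × 0.6522 = 32.6, taken as 30 v 33.
- Nervous system: 50 × 0.3043 = 15.2 and 50 × 0.1304 = 6.5, taken as 15 v 7.

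**Formula.** With Wilson limits (l, u) for each proportion p, the Newcombe 95% interval for d = p₁ − p₂ is:
- lower = d − √[(p₁ − l₁)² + (u₂ − p₂)²]
- upper = d + √[(u₁ − p₁)² + (p₂ − l₂)²]

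**Any TEAE, 30/50 v 33/50** (in points). The Wilson limits are 46.18 to 72.39 and 52.15 to 77.56, and d = −6.
- lower = −6 − √(13.82² + 11.56²) = −6 − 18.02 = −24.0
- upper = −6 + √(12.39² + 13.85²) = −6 + 18.58 = +12.6

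**Nervous system, 15/50 v 7/50.** The Wilson limits are 19.10 to 43.75 and 6.95 to 26.19, and d = +16.
- lower = 16 − √(10.90² + 12.19²) = 16 − 16.35, about −0.3
- upper = 16 + √(13.75² + 7.05²) = 16 + 15.45 = +31.45, shown as +31

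| Contrast | Difference | Newcombe 95% CI | Fisher p |
|---|---|---|---|
| 30/50 v 33/50 | −6 | −24.0 to +12.6 | 0.68 |
| 15/50 v 7/50 | +16 | −0.3 to +31 | 0.09 |
| 24/40 v 26/40 | −5 | −25.1 to +15.7 | 0.82 |
| 12/40 v 5/40 | +17.5 | −0.6 to +34.5 | 0.10 |

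At 50 per arm the Newcombe half-widths are (12.6 + 24.0)/2 = 18.3 points and (31.45 + 0.3)/2 = 15.9 points. The simple Wald half-widths are 18.9 and 15.9. Together they give roughly 16 to 19 points over incidences of 14% to 66%.

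For a true contrast of 30.4% v 13.0% with 50 per arm, Fisher's test would have about 48% power. This assumes a two-sided level of 0.05, since the SAP sets none for safety. A non-significant p-value would therefore not be reassuring.

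**The case against.** The strongest defence is that the trial is openly exploratory: "Since this is an exploratory trial no formal hypotheses are postulated. The data will be evaluated descriptively". Descriptive adverse event tables fit that aim. The safety endpoint's wording, unlike that of the efficacy endpoints, names no comparator, so per-arm incidence does estimate the endpoint as written. Anyone can also compute an interval later from the printed numbers, so nothing is lost. All of this stands, and it limits the weight of the point. It does not remove it, because intervals make no hypothesis claim and the same exploratory plan already gives them for efficacy, including in subgroups.

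Three stronger readings are tempting, and the documents do not support them.

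- *A reader might infer that safety rests on raw counts alone.* It does not. Patient percentages on the safety-set denominator are planned for every arm, and a test is foreseen in general terms.
- *A reader might infer that the sponsor dismissed the Phase IIa nervous system imbalance as unimportant.* Protocol 3.2 says that no clinically important differences were seen in the number and overall pattern of events by organ class. Infections ran the other way in that pattern (21.74% on active, 34.78% on placebo). Further detail is left to the Investigator's Brochure, which is not among these documents.
- *A reader might infer that treatment-related events cannot be read off the shells.* SAP 3.2.2.1 groups certain, probable and possible as related, and no shell has that combined row. But Table 14.5.1 counts each patient once, under the strongest relation, so the combined number of patients is the sum of three mutually exclusive rows.

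**Conclusion.** The point holds as a modest one. For a declared primary endpoint, the plan gives no between-arm estimate and no interval, and the one between-arm test that it announces for safety has no assigned variable or table. What the reader of the report would not see is an uncertainty of about 16 to 19 points either way on a risk difference at common event rates. That size rests on about 50 patients per arm in the safety set and on incidences between about 14% and 66%. The specific examples also assume rates like those of Phase IIa, whose denominators do not agree with the number stated as randomized.

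Nothing here affects the sample size, the analysis sets or the efficacy analyses, and no safety conclusion about the product follows from it. It is a cheap improvement and does not make the trial invalid.

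**What to change.** In SAP 3.4.7.1 and Table 14.5.1, add for each dose against placebo the risk difference in the proportion of patients, with a Newcombe 95% interval, for four rows: any TEAE, severe, serious, and leading to discontinuation. Label these as descriptive and unadjusted. In the same place, state that Fisher's exact test applies to these rows; otherwise delete its safety mention from SAP 3.4 and record that change from the protocol in SAP 1.3.

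A combined related-TEAE row using the SAP 3.2.2.1 grouping is optional, because it can already be derived.

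The cost is two comparison columns in one existing shell. That means 4 rows × 2 doses = 8 intervals (10 with the optional row), and as many p-values if Fisher's test is kept. No new data are needed. The downside is that a few more unadjusted intervals could be over-read, which the descriptive label should limit.

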3.4.7.2 Laboratory analyses

All safety laboratory parameters of hematology and clinical chemistry, as scheduled in Table 3, will be summarized descriptively, including their changes from baseline (see section 3.1). Shift tables of low, normal and high outcomes, determined with respect to the normal ranges, will be presented for each post-baseline visit, in comparison to the baseline outcome. Incidence of any clinically significant outcome, i.e. number of subjects having any clinically significant outcome during the trial will be presented for each laboratory parameter.

Urinalysis outcomes will be summarized by frequency counts and by shift tables of normal and abnormal outcomes. Incidence of clinically significant urinalysis parameter will be presented.

Individual subject's listings of all assessed safety laboratory parameters, scheduled or unscheduled, will be provided.

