5.3.2 Inclusion criteria

All of the following criteria have to be met for inclusion of a patient in this trial:

1. Participants legally competent to sign and give informed consent.
2. Adult male and female patients between 18 years and 70 years with moderate-to-severe chronic plaque psoriasis (diagnosed by Investigator):
 - a) PASI score ≥ 10 - ≤ 20 at baseline
 - b) BSA score: $> 10\%$
 - c) Stable disease duration of ≥ 6 months at the initiation of IMP.
 - d) topical therapy fails to control the disease
3. Body Mass Index (BMI) between 18.5 and 34.9 kg/m².
4. Women of childbearing potential (WCBP) must have a negative serum pregnancy test at Screening (Visit 1). In addition, sexually active WCBP must agree to use adequate contraception throughout the trial (see Section 3.2 for more details on adequate contraception):
 - a) A method with less than 1% failure rate OR
 - b) Abstinence
5. Post-menopausal women with spontaneous amenorrhea for at least 12 months and women on hormonal replacement therapy (HRT). The use of hormonal replacement therapy (HRT) during the trial is permitted, however for these patients an appropriate contraception method according to Inclusion Criterion 4 must be ensured. Sterilized women may be included (see Section 3.2 for more details on sterile definition)
6. Male patients who are sexually active with a female partner and are not surgically sterile (vasectomy performed at least six months prior to treatment) must agree to inform their female sexual partner to use an acceptable form of birth control as described in the informed consent form. For females, an acceptable method (Pearl Index < 1%) would be to use implants, injectable, combined oral contraceptives, some intrauterine devices, or be postmenopausal, be surgically sterile (hysterectomy, bilateral tubal ligation, or bilateral oophorectomy)
7. In good health as judged by the investigator, based on medical history, physical examination, serum chemistry, hematology and urinalysis
8. Patients must meet the following clinical laboratory criteria:

- White blood cell count $\geq 3.5 \times 10^9/L$
- Platelet count $\geq 100 \times 10^9/L$
- Serum creatinine $\leq 1.5 \times$ upper limit of normal (ULN); estimated glomerular filtration rate $> 60 \text{ mL/min}$
- Total bilirubin $\leq 1.5 \times \text{ULN}$
- Aspartate aminotransferase (AST) and alanine aminotransferase (ALT) $\leq 2.5 \times \text{ULN}$

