5.3.5.2 Criteria for discontinuing in the case of individual patients

Patients may withdraw from the entire trial including follow-up at any time without penalty and for any reason without prejudice to his or her future medical care.

The following criteria must lead to discontinuation from the clinical trial in individual patients:

- Patient withdraws informed consent

- Pregnancy (see section 7.4)
- Severe protocol violations that result in a significant risk to the patient's safety
- Emergence of the following AEs including:
 - a) Patient reports symptoms which are considered unacceptable by the patient or the Investigator or if any serious AE occurs that is judged as at least possibly related to the IMP by the Investigator
 - b) Abnormal laboratory value(s) confirmed by repeat measurements:
 - Elevated liver transaminases (AST/ALT) $\geq 3 \times$ ULN AND elevated bilirubin total bilirubin $\geq 2 \times$ ULN
 - Elevated serum creatinine $\geq 2 \times$ ULN

The following criteria may lead to discontinuation from the clinical trial in individual patients:

- Use of prohibited concomitant medication as defined in section 5.4.5.

In all cases, the reason(s) for withdrawal, and the primary reason, must be recorded on the electronic data capture (EDC) system / electronic case report form (eCRF). If a patient is prematurely withdrawn from the IMP for any reason, the Investigator must make every effort to perform the evaluations described for the End of Treatment and Follow-up Visits. The Investigator should contact the Medical Monitor, whenever possible, to approve withdrawal of patients in advance.

If a patient withdraws consent and still agrees to undergo a final examination, it will be documented on the eCRF and the patient record.

A patient may also be withdrawn from the IMP by the Sponsor, Regulatory Authorities, or Independent Ethics Committees (IECs) / Institutional Review Boards (IRBs).

Patients who are withdrawn from the trial will be not replaced.

Protocol violation, failure to comply with the trial stipulations/poor compliance may lead to discontinuation from the clinical trial in individual patients.

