Min , max	XXX , XXX	XXX , XXX	XXX , XXX

¹ Baseline: Last observation collected prior to first dose of any IMP, i.e. Day 1 assessment or, if missing, Screening assessment.

Source data: <DATASET> <DATE>
Program: <SAS PROGRAM> <DATE>

Table 14.6.2: Hematology – Hematocrit [%]: Summary (SES)
Analog to Table 14.6.1 for Hematocrit

Table 14.6.3: Hematology – Mean corpuscular hemoglobin [pg]: Summary (SES)
Analog to Table 14.6.1

Table 14.6.4: Hematology – Mean corpuscular HGB concentration [g/dL]: Summary (SES)
Analog to Table 14.6.1

Table 14.6.5: Hematology – Mean corpuscular volume [fL]: Summary (SES)
Analog to Table 14.6.1

Table 14.6.6: Hematology – Erythrocytes [$10^{12}/L$]: Summary (SES)
Analog to Table 14.6.1

Table 14.6.7: Hematology – Leukocytes [$10^9/L$]: Summary (SES)
Analog to Table 14.6.1

Table 14.6.8: Hematology – Platelets [$10^9/L$]: Summary (SES)
Analog to Table 14.6.1

Table 14.6.9: Hematology – Eosinophils [$10^9/L$]: Summary (SES)
Analog to Table 14.6.1

Table 14.6.10: Hematology – Lymphocytes [$10^9/L$]: Summary (SES)
Analog to Table 14.6.1

Table 14.6.11: Hematology – Neutrophils [$10^9/L$]: Summary (SES)
Analog to Table 14.6.1

Table 14.6.12: Hematology – Eosinophils/Leukocytes [%]: Summary (SES)
Analog to Table 14.6.1

Table 14.6.13: Hematology – Lymphocytes/Leukocytes [%]: Summary (SES)
Analog to Table 14.6.1

Table 14.6.14: Hematology – Neutrophils/Leukocytes [%]: Summary (SES)
Analog to Table 14.6.1

Table 14.6.15: Coagulation – International normalized ratio of prothrombin time: Summary (SES)
Analog to Table 14.6.1

Table 14.6.16: Clinical chemistry – Alkaline phosphatase [U/L]: Summary (SES)
Analog to Table 14.6.1

Table 14.6.17: Clinical chemistry – Alanine aminotransferase [U/L]: Summary (SES)
Analog to Table 14.6.1

Table 14.6.18: Clinical chemistry – Aspartate aminotransferase [U/L]: Summary (SES)
Analog to Table 14.6.1

Table 14.6.19: Clinical chemistry – Bilirubin [mg/dL]: Summary (SES)
Analog to Table 14.6.1

Table 14.6.20: Clinical chemistry – Creatinine [mg/dL]: Summary (SES)
Analog to Table 14.6.1

Table 14.6.21: Clinical chemistry – C reactive protein [mg/L]: Summary (SES)
Analog to Table 14.6.1

Table 14.6.22: Clinical chemistry – Gamma glutamyl transferase [U/L]: Summary (SES)
Analog to Table 14.6.1

Table 14.6.23: Urinalysis – Occult blood: Summary (SES)
(Part 1 of 2)

Urinalysis – Occult blood	MP1032 300 mg bid (N = XX)	MP1032 150 mg bid (N = XX)	Placebo bid (N = XX)
Screening			
N	XXX	XXX	XXX

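### No by-arm table counts liver and kidney laboratory results on the ×ULN scale or by the protocol's joint liver criterion, and the three-category shift tables cannot show worsening within 'high'

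*SAP*

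**What the plan says.** SAP 3.4.7.2 plans four things for haematology and clinical chemistry:

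- descriptive summaries of values and of changes from baseline;
- shift tables against baseline: "Shift tables of low, normal and high outcomes, determined with respect to the normal ranges, will be presented for each post-baseline visit";
- for each parameter, the number of patients with any clinically significant result;
- individual listings of every value, scheduled or not.

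The clinical chemistry shells in the SAP appendix (Tables 14.6.16 to 14.6.22, modelled on Table 14.6.1) hold N, mean, SD, median, minimum and maximum, by arm and visit, in raw units. The appendix has no shell for the laboratory shift tables or for the clinically significant counts.

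Protocol 5.3.5.2 lists two laboratory criteria that must lead to discontinuation, under the condition "Abnormal laboratory value(s) confirmed by repeat measurements". They are "Elevated liver transaminases (AST/ALT) $\geq 3 \times$ ULN AND elevated bilirubin total bilirubin $\geq 2 \times$ ULN" and "Elevated serum creatinine $\geq 2 \times$ ULN". Protocol 5.3.2, criterion 8, lets patients in with AST/ALT up to 2.5×ULN, total bilirubin up to 1.5×ULN and creatinine up to 1.5×ULN.

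Under SAP 3.5.2, applied to unscheduled visits by 3.5.3, an off-schedule value enters the statistics only if a neighbouring planned visit is missing. Otherwise it appears in listings alone. Safety values taken at withdrawal are reported with Day 84.

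**The concern.** The protocol thinks about liver and kidney safety in multiples of ULN and, for the liver, in two parameters jointly. The SAP tabulates on a scale with one upper cut, at 1×ULN, and always one parameter at a time. The two scales do not meet. A reader of the report who asks how many patients in each arm reached 3×ULN, or met the combined liver criterion, or worsened after entering above ULN, will find no table that answers.

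Safety is part of the primary objective. Earlier exposure, as the protocol introduction describes it, was 300 mg twice daily for 7 days in volunteers and 100 mg twice daily for 42 days in patients. This trial gives 150 or 300 mg twice daily for 12 weeks, so a clear comparison by arm of marked laboratory changes is worth having.

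**Working it through.** The plan states no figure for laboratory safety (its sample-size statement concerns responder rates), so there is nothing to reproduce. The check sets the scales side by side.

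**1. Entry limit, stopping level and shift cut.** Entry limits come from protocol 5.3.2 and stopping levels from 5.3.5.2. The shift cut is the normal range in SAP 3.4.7.2.

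| Parameter | Entry limit (×ULN) | Stopping level (×ULN) | Ratio | Upper shift cut (×ULN) |
|---|---|---|---|---|
| AST/ALT | 2.5 | 3, only jointly with bilirubin | 3/2.5 = 1.20 | 1 |
| Total bilirubin | 1.5 | 2, only jointly with AST/ALT | 2/1.5 = 1.33 | 1 |
| Creatinine | 1.5 | 2 | 2/1.5 = 1.33 | 1 |

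For a patient who enters above ULN, the whole path from the entry value to the stopping level and beyond lies inside the single category 'high'.

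**2. What the shift table records.**

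| Baseline (×ULN) | Post-baseline (×ULN) | Cell |
|---|---|---|
| ALT 2.4 | 2.4 | high to high |
| ALT 2.4 | 10 | high to high |
| Creatinine 1.5 | 2.0 | high to high |
| ALT normal | 1.1 | normal to high |
| ALT normal | 10 | normal to high |

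The first three rows cannot be told apart as 'changed' or 'unchanged', and the last two cannot be told apart at all.

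**3. The joint liver criterion.** Take two constructed arms of 50. In each, two patients have ALT 3.5×ULN, two have bilirubin 2.2×ULN, and all other values are 0.7×ULN. In arm A the same two patients have both elevations; in arm B they are different patients.

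- ALT mean, both arms: (2×3.5 + 48×0.7)/50 = 40.6/50 = 0.812
- Bilirubin mean, both arms: (2×2.2 + 48×0.7)/50 = 38.0/50 = 0.76
- Bilirubin SD, both arms: √[(2×1.44² + 48×0.06²)/49] = √(4.32/49) = 0.297
- Maxima in both arms: 3.5 and 2.2. Number 'high' in both arms: 2 and 2
- Patients with both ALT ≥3 and bilirubin ≥2: **2 in A, 0 in B**

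The single-parameter summaries are identical while the joint count differs. The chosen values are for the logic only and are not a forecast.

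**4. Off-schedule samples.** The criteria need a repeat measurement. If the repeat is taken between two planned visits that both took place, SAP 3.5.2 sends it to the listings only. A confirming value, or a peak, can then be absent from every by-visit table.

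**5. What a count could say.** With about 50 patients per arm, zero cases gives a one-sided 95% upper bound of 1 − 0.05^(1/50) = 5.8%. For the two active arms together it is 1 − 0.05^(1/100) = 3.0%. For assumed true rates of 1%, 2% and 5% (the documents give none), the chance of at least one case in an arm, 1 − (1 − p)^50, is 0.395, 0.636 and 0.923. The count would be coarse, but it would be readable and comparable between arms.

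**The case against.** The strongest reply is that a threshold case has several other ways into the report. Protocol 5.3.5.2 places the laboratory criteria among adverse events that must lead to discontinuation, and protocol 7.1 counts an abnormal laboratory finding as a possible adverse event. If the protocol is followed, a confirmed case after first dose is a treatment-emergent event tabulated by arm. It should also appear in the Table 14.5.1 row for events that led to discontinuation, in the listing of such patients, and in disposition Table 14.1.3. The shells show the maximum value and maximum change, the SAP also plans clinically significant counts, and the listings hold everything. In a trial of about 150 patients, the joint criterion can be found by hand.

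That stands as far as it goes. A reader might infer that patients crossing the thresholds would be invisible in the report; the documents do not support this.

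It does not close the gap. A preferred term need not name the threshold or the multiple of ULN. The stopping-criteria row in Table 14.1.3 pools all criteria and competes with the adverse-event row as the recorded reason. A maximum shows that at least one extreme value exists at an analysed visit, in raw units, but not how many patients had one or whether bilirubin rose in the same patient. 'Clinically significant' has no numeric definition and is per parameter. A listing is not a comparison by arm.

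Entry also requires an estimated glomerular filtration rate above 60 mL/min, which may keep the number entering with raised creatinine small.

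**Conclusion.** The concern holds in a limited form. SAP 3.4.7.2 contains no by-arm count of patients by ×ULN level and none of the joint AST/ALT and bilirubin criterion. Its shift tables cannot show worsening within 'high' or separate slight from marked elevation. This is a worthwhile, cheap improvement to an exploratory trial's safety reporting, not an error or a contradiction.

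No numerical size can be attached: the documents do not say how many patients enter above ULN or how often such rises are expected. The conclusion assumes only that 'high' means above the upper limit of the normal range.

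Two other stronger readings should be resisted. A reader might take AST/ALT ≥3×ULN or bilirubin ≥2×ULN as protocol stopping thresholds on their own; the protocol requires both, confirmed. A reader might also take the missing shells to mean that the shift and clinically significant tables were dropped. The SAP text still requires them, so this is a programming gap only.

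**What to change.** In SAP 3.4.7.2, add one descriptive table by arm in the safety evaluation set:

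- the worst post-baseline ×ULN category for AST/ALT, total bilirubin and creatinine, over all scheduled and unscheduled samples, against baseline ×ULN category;
- the number of patients meeting the protocol 5.3.5.2 criteria as written: AST/ALT ≥3×ULN and bilirubin ≥2×ULN in the same patient, and creatinine ≥2×ULN;
- for each of these, any-occurrence and confirmed-by-repeat counts shown separately;
- a footnote labelling single-parameter liver counts as descriptive and not as protocol stopping thresholds.

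State that this table uses off-schedule samples despite SAP 3.5.2. As housekeeping, add shells for the shift and clinically significant tables that the text already requires.

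The cost is SAP wording and one extra table from data already collected. Sample size, patient care and the protocol's criteria are unchanged.
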